Sample size and Power: Given the potentially large number of statistical tests that will be performed to assess SVs, it will be necessary to set the p-value for declaring statistical significance quite low. However, unlike GWAS studies, the number of tests to be performed cannot be specified *a priori*. For illustrative purposes, sample size requirements are presented for a p-value threshold of 5×10^{-5} (accounting for 1,000 comparisons). However, this threshold will be reconsidered when SV data are available, and can be used to estimate the number of comparisons that will actually be made. Minimum sample size requirements to achieve adequate power (>80%) to detect genotype relative risks ranging from 1.2-2.0 for common variants (minor allele frequency (MAF)≥0.10) and, from 1.2-5.0 for rare variants (MAF=0.001 and 0.01), under an additive model of inheritance, assuming a 1:4 case-control ratio are provided in Table 2. These estimates were obtained using the computer program Quanto (version 1.2.3, Gauderman and Morrison, http://hydra/usc.edu/gxe).

Table 2: Minimum sample size requirements	for SV analyses using
---	-----------------------

 $p < 5x10^{-5}$ as the threshold for significance.

Genotype Relative Risk	Frequency of High Risk Allele						
	0.001	0.01	0.10	0.20	0.30	0.40	0.50
1.2	404,600	40,900	4,600	2,600	2,100	1,800	1,800
1.4	108,200	11,000	1,200	740	590	540	540
1.6	51,200	5,200	610	370	280	280	280
1.8	30,500	3,100	310	230	190	180	180
2.0	20,600	2,100	355	160	130	130	130
3.0	6,400	660				1	
4.0	3,400	350					
5.0	2,200	230					

F.3 Candidate Gene, Whole-Exome, And Whole-Genome Sequence Analyses

Evaluation of sequence variants will be based upon comparison with publically available sequence data. In general, these analyses will focus on identification of rare variants and, in particular, variants that are identified in as few as one case and are unobserved among a large number of control sequences. Power calculations are not provided for the proposed sequence analyses, since the identification of rare variants found only in cases is of interest regardless of the associated p-value.

F.3.1 Analysis and annotation of the exome or MIPS sequencing data

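### Table 2 (F.2): at allele frequency 0.10 the required sample rises from 310 at relative risk 1.8 to 355 at 2.0, which cannot be right; two other cells are mildly low

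*Protocol*

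**What the plan says.** Protocol section F.2, under Sample size and Power, sets an illustrative threshold of 5x10^-5, "accounting for 1,000 comparisons", and says that it will be revisited once structural-variant data exist. The sizes are described thus: "Minimum sample size requirements to achieve adequate power (>80%) to detect genotype relative risks ranging from 1.2-2.0 for common variants". A wider range of relative risks, up to 5.0, is given for rare variants. The calculation is made "under an additive model of inheritance, assuming a 1:4 case-control ratio are provided in Table 2", and the software is named: "These estimates were obtained using the computer program Quanto (version 1.2.3".

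The allele-frequency columns run 0.001, 0.01, 0.10, 0.20, 0.30, 0.40 and 0.50. The two rows at issue, each starting with the relative risk, are:

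- "1.8 30,500 3,100 310 230 190 180 180"
- "2.0 20,600 2,100 355 160 130 130 130"

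The third size in each row belongs to frequency 0.10. Read downwards from relative risk 1.2 to 2.0, that column is 4,600, 1,200, 610, 310, 355. The caption does not say whether N counts cases or cases plus controls. The opening paragraphs of section F state that modest effects need very large samples and that stronger effects need much smaller ones.

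**The concern.** At a fixed allele frequency, significance level, power and control ratio, the required number of cases must fall as the relative risk moves further above 1 over this range. The step from 310 to 355 reverses that order, and no other column of Table 2 rises. At least one of the two figures is therefore wrong before anything is calculated, and the table contradicts the principle that section F says it illustrates.

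The sizes are offered as the minimum for more than 80% power. Section F also says that more homogeneous subsets will be analysed as numbers allow, and Table 2 is the only place in the Protocol that shows what size a structural-variant analysis needs. A figure that is too low makes a subset look adequate when it is not; a figure that is too high does the reverse.

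**Working it through.** **Inputs from F.2.** Threshold 5x10^-5 = 0.05/1,000; power 80%; additive model; 1 case to 4 controls.

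**Assumptions.** The Protocol does not state sidedness or the disease prevalence used. I take a two-sided test, a rare disease, Hardy-Weinberg genotype frequencies, and relative risks of 1, R and R² for 0, 1 and 2 risk alleles (log-additive).

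**Formula.** Let p0(g) be the genotype frequencies in controls and p1(g) those in cases, with p1(g) proportional to p0(g)·R^g. The expected likelihood-ratio statistic per case (with its four controls) is

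L = 2 { Σ p1 ln[p1/(p1+4p0)] + 4 Σ p0 ln[4p0/(p1+4p0)] − ln(1/5) − 4 ln(4/5) }.

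Then N cases = (z_α/2 + z_power)² / L = (4.056 + 0.842)² / L = 23.98 / L. Power at a printed size n is Φ(√(nL) − 4.056).

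**Does this reproduce the plan's own figures?**

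- Table 1: the same calculation at 1:1 and two-sided 10^-8 returns 24 of 25 cells exactly and the other within 1 (675 against 676).
- Table 2: 37 of 41 cells agree within 3%. At the printed sizes these 37 give 78.2% to 81.4% power, which is what rounding would produce.
- N is therefore the number of cases.

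**The two cells in the wrong order** (frequency 0.10; controls 0.81, 0.18, 0.01):

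- R = 1.8: cases 0.694, 0.278, 0.028; L = 0.06475; N = 23.98/0.06475 = 370.4, so 371. Printed 310 (−16%). Power = Φ(√(310×0.06475) − 4.056) = Φ(0.424) = 66%.
- R = 2.0: cases 0.669, 0.298, 0.033; L = 0.09392; N = 255.4, so 256. Printed 355 (+39%). Power = Φ(√(355×0.09392) − 4.056) = Φ(1.718) = 96%.

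**The two milder cells:**

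- Frequency 0.10, R = 1.4: L = 0.019055; N = 1,258.7, so about 1,260. Printed 1,200 (−4.7%). Power 77%.
- Frequency 0.30, R = 1.6: L = 0.080908; N = 296.4, so 297. Printed 280 (−5.5%). Power 76%.

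After correction the 0.10 column falls steadily: 4,597, 1,259, 609, 370, 255 (to the nearest whole case).

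**Can another setting explain 310 and 355?** Cases required at frequency 0.10:

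| Setting | R = 1.8 | R = 2.0 |
|---|---|---|
| Printed | 310 | 355 |
| Prevalence 0.008, effects as odds ratios | 372 | 257 |
| One-sided test | 346 | 238 |
| Trend test | 357 | 245 |
| Allele-count comparison | 355 | 243 |
| Risk-additive model | 419 | 295 |
| Dominant model | 465 | 325 |
| 1:1 ratio | 621 | 431 |
| 1:10 ratio | 320 | 219 |

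Every setting asks for fewer cases at 2.0 than at 1.8. None gives 310 in the first column of results or 355 in the second. The computed 370 and 255 each differ from the printed 310 and 355 by one digit, so transcription slips are a likely cause.

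**The case against.** **The table is illustrative.** F.2 says so and says that the threshold will be reconsidered. Accrual is set only as thousands of participants, there are no planned stopping rules, and no decision is tied to a cell. This stands, and it limits the severity. It does not excuse figures that are wrong at the threshold the table itself uses. A reader might infer that the choice of subsets to analyse will go wrong. The documents do not support that: they never say the table will be used to choose subsets, and at these two cells the error matters only for groups of roughly 255 to 370 cases.

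**The two smaller discrepancies are a matter of degree.** This is largely right. The 3% tolerance is my choice, and some accepted cells also fall short of 80%: 1,800 at frequency 0.40, relative risk 1.2, and 130 at frequency 0.30, relative risk 2.0, each give 78.2%. The 1,200 cell also depends on an unstated input. If the effects are read as true relative risks at a prevalence of 8 per 1,000, the need falls to about 1,237, a gap of 3%. Even so, neither figure is a rounding of the computed value (1,300 and 300 would be).

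**The text was extracted from PDF.** A stray digit appears in the row for relative risk 3.0, so a reading error cannot be wholly excluded. The original table should be checked first.

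**Fisher's exact test.** F.2 names it, and applied to carriers it gives about 77% to 78% power in the rare-variant cells for relative risks 3 to 5. A reader might infer that those cells are wrong too. They are not: Table 2 states its basis as an additive model in Quanto, and F.2 lists Fisher's test as only one of several options. Nor is Table 1's unit in doubt, since F.1 says that its calculations rest on case-parent triads.

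**Conclusion.** The point holds for Table 2. The reversal at frequency 0.10 is wrong on its face and contradicts section F's own statement. Under the stated inputs both figures are off: about 371 cases are needed where 310 is printed (66% power) and about 256 where 355 is printed (96% power). The exact replacements assume a two-sided test and a rare disease, an assumption supported by the agreement of the other 37 cells; the reversal itself does not depend on it. The 1,200 and 280 cells are mildly low, at about 77% and 76% power, and the first is sensitive to prevalence.

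Severity is minor to moderate. It would go too far to treat the whole power basis as unsound: Table 1 and 37 of the 41 cells in Table 2 reproduce, and the broad message that modest effects need very large samples is unaffected.

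**What to change.** 1. Compare Table 2 with the original table and the Quanto output to see whether 310 and 355 are transcription slips.
2. Rerun and correct the four cells: about 371 (frequency 0.10, relative risk 1.8), 256 (0.10, 2.0), 1,260 (0.10, 1.4) and 297 (0.30, 1.6). Rounded upward these could read 380, 260, 1,260 and 300.
3. Since the entries are called minimum sizes, round the others upward too so that each delivers the stated power. Examples are 2,600 at frequency 0.20, relative risk 1.2 (2,647 needed), 1,800 at 0.40, 1.2 (1,847 needed), and 130 at 0.30, 2.0 (134 needed).
4. State in the caption that N is the number of cases, with four controls each. At 1:4 the other reading differs fivefold. Also state the sidedness and the prevalence used.

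The cost is one corrected table and caption. Some sizes become slightly less favourable; design, accrual and analysis do not change.

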Current understanding of the etiology of pediatric cardiovascular disorders is limited. The etiology of congenital heart disease is multifactorial and consists of a combination of environmental, teratogenic, and genetic causes [9-18]. Furthermore, both genetic and environmental factors have been proposed to act as disease modifiers, accounting for the wide variation in phenotypic expression and clinical outcomes of these disorders [11-18]. To date however, few specific genetic or environmental causative factors have been identified. It is estimated that ~11% of CHD patients have some form of chromosomal abnormality causing cardiac malformation [1]. This includes patients with aneuploidy (such as trisomy 13, 18, and 21, as well as Turner Syndrome) who have an elevated prevalence of CHD as compared to the general population [19, 20]. Chromosomal structural abnormalities, such as monosomy 22q11, are a second significant genetic contributor to CHD [9]. More recently, disease-related single-gene defects have been identified in a small number of cases, including mutations in the transcription factors *NKX2.5*, *ZIC3*, *JAG1* and *NOTCH1* [11, 21-25]. Despite these recent discoveries, the cause of the majority of cases of CHD remains largely unknown despite strong evidence of a significant genetic component [9].

The analysis of CHD genetics is complicated by the limited correlation between the genetic defect and specific CHD phenotype. In particular:

- 1) Similar cardiac defects may be caused by more than one genetic alteration (genetic heterogeneity) [26].
- 2) One gene may cause more than one CHD phenotype (variable expressivity) [26].
- A person without CHD may carry a disease-causing gene mutation (reduced penetrance).
- 4) One or more genes may be causal for CHD associated with chromosomal alterations [9, 27].

5) Single gene defects can cause CHD with or without being recognized as a clinical syndrome [23].

Analyses are further complicated by the likelihood that phenotypic variability results from genetic modifiers, the interaction of genes and environment, and/or stochastic effects.

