We will use a mix of publicly available and privately developed tools. First, we will map sequence reads to the reference human genome. Reads outside of the targeted sequences will be discarded and statistics on coverage will be collected from the remaining reads. Once the likely mapping locations are identified, the reads will be aligned allowing gaps to the reference genome using BWAmem and comparable software packages in order to identify indels. Potential variants will be called using TERRA, Genome Analysis Toolkit or similar platforms, as well as custom tools already developed in-house at several of the participating centers. We will identify known variants from dbSNP, publicly available genomes and exomes, including the 1000 Genomes Project, TOPMed, UK Biobank, and the Genome Aggregation Database, and exomes previously sequenced at the participating centers.

Sequence variants will be filtered for quality, using criteria such as [30]:

- a. Calls with a Phred-like quality score of less than 45 will be excluded
- b. Reads supporting the major and minors alleles should have different start and end points
- c. Total reads at variant bases should be > 10

For remaining sequence variants lying within exons, their predicted effect on the encoded protein will be determined and deleterious effects predicted, e.g., with Polyphen or predicted premature termination of the protein. The degree of evolutionary conservation will be assessed for nonsynonymous changes using phyloP or similar scores calculated from multiple alignments of >40 vertebrate species, which are available from the University of California Santa Cruz genome browser (http://genome.ucsc.edu) as well as comparison with invertebrate orthologues.

Rare exonic variants that alter conserved residues and are predicted to have significant impact on protein function in genes will be studied further, such as those in genes that are expressed during

development and/or in cardiac tissues. Variants per gene, or per gene class, will be compared with overall or ethnically matched control samples to determine any association with CHD. When appropriate, segregation analyses within the family will be assessed and Lod scores determined. In addition, sequence analyses of that gene in unrelated affected samples will be performed, and newly discovered variants will be examined as above. The significance of rare variants found only in affected cases will be assessed by p-values.

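### F.3 sets p-values aside for rare variants seen only in cases, F.3.1 assesses the same variants by p-values, and for a once-seen variant that p-value only restates the sample sizes.

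*Protocol*

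**What the plan says.** Section F.3 concentrates on rare variants, in particular "variants that are identified in as few as one case and are unobserved among a large number of control sequences". It gives no power calculation for the sequence analyses, and its stated reason is that "the identification of rare variants found only in cases is of interest regardless of the associated p-value".

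Section F.3.1, on exome and MIPS data, ends its account of rare exonic variants with "The significance of rare variants found only in affected cases will be assessed by p-values". It names no test for that assessment.

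The same paragraph of F.3.1 holds three other lines of evidence:
- an aggregate test: "Variants per gene, or per gene class, will be compared with overall or ethnically matched control samples to determine any association with CHD";
- family evidence: "When appropriate, segregation analyses within the family will be assessed and Lod scores determined";
- sequencing of the same gene in unrelated affected samples.

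Section C.3 adds the case-parent triad design for de novo changes, and resequencing of candidates in many patients to support or refute causality. The Background (section A) lists reduced penetrance among the complications: a person without CHD can carry a causal mutation.

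**The concern.** The two sentences give opposite roles to the p-value for one class of variant. In F.3 its irrelevance is the reason for omitting power. In F.3.1 it is the measure of significance. Someone analysing the data could cite either sentence, and could choose after seeing the results.

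The p-value in question also carries almost no information at the single-variant level. If the variant appears once, in a case, the p-value is fixed by how many cases and controls were sequenced. A causal variant and a chance variant get the same number. Making the control database larger makes every such variant look more significant.

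There is a selection problem as well. If variants are picked because no control has them, and are then tested against those controls, the control count is zero by construction. The comparison is tilted toward association before any data on the gene as a whole are considered.

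Sequencing is one of the routes named in the primary aim, so this affects what may be called a discovered CHD gene.

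**Working it through.** **Inputs**
- Case:control ratio 1:4: stated in F.2 for structural variants only, used here as one scenario.
- Cases: the Summary Table says only that thousands of participants will be accrued. Assumed n = 3,000 to 10,000.
- Controls: public databases, no size given. Assumed m = 50,000 to 500,000.
- Gene count: not given. Assumed 20,000, so 0.05/20,000 = 2.5x10^-6.
- Thresholds in the protocol: about 10^-8 for GWAS (F.1), and an illustrative 5x10^-5 for structural variants (F.2). Neither is assigned to sequencing.

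**The plan's own figures.** F.3 states no sample size, power or alpha, so there is nothing to reproduce for sequencing. The nearest figure, the F.2 threshold, does reproduce: 0.05/1,000 = 5x10^-5.

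**Step 1: one case carrier, no control carriers.** With a single carrier among n + m people, the one-sided Fisher p is the chance that the carrier is a case:

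p = n/(n+m)

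| Cases : controls | p |
|---|---|
| 1:4 | 0.20 |
| 1:10 | 0.091 |
| 1:50 | 0.0196 |
| 1:100 | 0.0099 |
| 1:500 | 0.0020 |

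The two-sided p is the same at all these ratios. At the extremes of the assumed sizes:
- smallest: 3,000/503,000 = 0.006
- largest: 10,000/60,000 = 0.167

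Controls needed per case for this p to reach a threshold a are 1/a - 1: about 20,000 for 5x10^-5, about 400,000 for 2.5x10^-6, and about 100 million for 10^-8. The most generous assumed ratio is 500,000/3,000, or about 167.

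**Step 2: k carriers in one gene, all in cases.** Here p = C(n,k)/C(n+m,k), approximately (n/(n+m))^k. The smallest k giving p < 2.5x10^-6:
- n = 3,000, m = 500,000: 0.00596^2 = 3.6x10^-5 misses and 0.00596^3 = 2.1x10^-7 reaches it, so k = 3.
- n = 10,000, m = 50,000: (1/6)^7 = 3.6x10^-6 misses and (1/6)^8 = 6.0x10^-7 reaches it, so k = 8.

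Even 10^-8 is attainable at gene level: 12 case-only carriers at 1:4, or 4 at 1:100.

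**Step 3: why both groups must be counted.** Take a hypothetical gene with no association, with 60 variants each seen once, at 1:4. The expected split is 60 x 0.2 = 12 in cases and 48 in controls, which is the same carrier rate in each group. If only the variants unseen in controls are kept, the table becomes 12 against 0 and the nominal p is 0.2^12 = 4.1x10^-9. The selection alone produces it. The counts in Step 2 are therefore valid only if control carriers of equally rare variants in the gene are counted too and turn out to be zero.

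**Step 4: absence is a moving criterion.** An allele at population frequency f is absent from m controls with probability about exp(-2mf). For an assumed f = 10^-5:
- m = 50,000: exp(-1) = 37%
- m = 150,000: exp(-3) = 5%
- m = 500,000: exp(-10) = 0.005%

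Whether such an allele counts as unobserved depends mainly on database size.

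**The case against.** The strongest reply is that the two sentences describe two stages. F.3 says that finding such variants is of interest. F.3.1 assesses significance later, after filtering, annotation, the gene comparison, segregation analysis and follow-up in other affected samples. Section F also calls its methods examples of current approaches, and a named test and exact threshold commonly sit in a SAP. Part of this stands. The staged reading is possible, and the missing threshold is not counted here as a fault. But the text never draws the distinction, and the conflict lies in what the protocol states, so a SAP would not remove it.

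Several stronger readings are tempting, and the document does not support them:
- **That no sequencing analysis could reach a stringent level.** A reader might infer this from Step 1. The once-seen variant is the lower bound of a stated focus and is not the only unit tested. The per-gene and per-gene-class comparison can reach such levels, and Lod scores and triads add further routes.
- **That a gene scan would run at 5x10^-5.** Over an assumed 20,000 genes that would give a family-wise error of 63%. F.2 offers the value as an illustration for 1,000 structural-variant comparisons and says "this threshold will be reconsidered when SV data are available". Nothing carries it over to a gene scan.
- **That variants with reduced penetrance are thrown away.** Absence from controls is a focus in F.3. No rule excludes a variant seen in a control.
- **That the reference set contains the study's own cases or parents.** F.3.1 includes "exomes previously sequenced at the participating centers" among its sources for identifying known variants. It does not say that participants are among them, or that known variants are removed.

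**Conclusion.** The concern holds in a limited form. F.3 and F.3.1 give unreconciled instructions on the p-value for rare case-only variants. For a variant seen in one case and no controls, the p-value is n/(n+m), whatever the biology: 0.20 at 1:4, and 0.006 to 0.17 at the assumed sizes. It cannot separate causal from chance variants or support a discovery claim, and testing variants selected for absence in controls is biased toward association.

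The gene-level comparison already in F.3.1 is a sound basis for inference if it counts both groups alike. About 3 to 8 carriers, all in cases, would reach 2.5x10^-6. The 0.006 to 0.17 range and the carrier counts rest on assumed case and control numbers, and the threshold on an assumed gene count. The formula n/(n+m) does not depend on any of these.

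This should be corrected because it changes what can be concluded from sequencing. It is not a flaw that invalidates the study: the cohort is observational, and the repair uses analyses the protocol already describes.

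**What to change.** 1. In F.3, remove the rationale that the p-value does not matter. Say instead that single case-only variants are candidates reported descriptively, so no power is claimed for them.
2. In F.3.1, remove the sentence that assesses case-only variants by p-values.
3. Confine p-value inference to the gene or gene-class comparison, plus a test of de novo enrichment in the triads.
4. In the gene-level comparison, define qualifying rare variants by an allele-frequency ceiling and count carriers in both cases and controls. Do not require absence from controls: the Background recognises unaffected carriers, and absence depends on database size.
5. Apply a multiplicity-adjusted gene-level threshold, with its exact value given in the protocol or the SAP. With 20,000 genes tested it would be 2.5x10^-6.

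The cost is rewording plus modest analysis work to count carriers in the control data on the same definition. The downside is that fewer genes can be claimed than with unadjusted p-values.
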